#### 5.2.1. Arm A: Ibrutinib PO and Obinutuzumab IV

**Ibrutinib** will be given orally at a dose of 420 mg daily (3 capsules). There is no prospective limitation to the duration of ibrutinib therapy, and should be administered until progression or unacceptable toxicity.

The first dose of ibrutinib will be taken in the clinic, after which ibrutinib will be issued to the subject as an ongoing 28-day supply for home administration. On Day 1, ibrutinib will be given as soon as the subject comes into clinic. Pre-medications and obinutuzumab will then be given as outlined below.

**Obinutuzumab** will be administered intravenous at a fixed dose of 1000 mg over 6 cycles: given on Days 1+2 (100 mg on Day 1 and 900 mg on Day 2), Day 8 (1000 mg) and Day 15 (1000 mg) of Cycle 1 and on Day 1 (1000 mg) only of subsequent cycles, for up to 6 cycles.

Intravenous obinutuzumab will be administered per Section 5.3.2.3.

In the event of permanent discontinuation of concomitant obinutuzumab therapy, treatment with ibrutinib will continue as originally scheduled.

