**10.8.1. Adverse Events (AEs)**

Adverse events (AEs) will be graded by the Investigator according to the NCI CTCAE v4.03 for non-hematological AEs. Hematologic toxicity will be assessed by the IWCLL 2008 criteria for grading hematologic toxicity in CLL studies. Verbatim descriptions of AEs will be coded using the current version of the Medical Dictionary for Regulatory Activities (MedDRA). Adverse events that started from the date of the first dose of the first study drug up to 30 days after the date of the last dose of the last study drug, or the first date starting new anticancer therapy, whichever is earliest, are considered treatment-emergent except treatment related AEs. Any treatment related AE will be considered treatment-emergent regardless of the start date of the event. Any event that is present at baseline but worsens in severity or is subsequently considered treatment-related by the investigator will also be considered as treatment-emergent. All-treatment emergent AEs will be summarized by treatment arm. The incidence rates of treatment-emergent AEs will be summarized by System Organ Class (SOC), preferred term, toxicity grade, and relationship to study drug. In addition, SAEs, Grade 3 or above AEs, AEs leading to study treatment discontinuation, delay, reduction, or interruption, AEs leading to death, and events of special interest will be summarized. Multiple occurrence of the same event in a given subject will be counted once at the maximum severity and strongest relationship to study drug.

AEs leading to death and non-fatal SAEs will be listed by subject and tabulated by preferred term.

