
Chlorambucil will be administered orally at a dose of 0.5 mg/kg body weight, on Days 1 and 15 of each cycle, for up to 6 cycles.

Obinutuzumab will be administered the same as in arm A.

Upon IRC-confirmed progression, subjects in Arm B have the opportunity to receive ibrutinib monotherapy orally at a dose of 420 mg daily (3 capsules) continuously until determined otherwise by the investigator.

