1.4. Sample Size Determination

This study was powered for testing the primary hypothesis of this study.

The sample size is calculated based on the assumptions:

- Randomization ratio of 1:1
- Median PFS of 27 months for Arm B (chlorambucil in combination with obinutuzumab)
- Target hazard ratio of 0.55, which corresponds to median PFS of 49.1 months for Arm A (ibrutinib combined with obinutuzumab).

On this basis, 94 PFS events provide 80% power to achieve a statistical significance level of 5% (2-sided) under exponential distribution. With an estimated accrual rate of 18 subjects per month, approximately 212 eligible subjects were to be enrolled to observe 94 PFS events in about 36 months from the first subject randomized.

The sample size and power calculations were calculated using the software package, East (Cytel Software Corp, Cambridge, MA) version 6.3.

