5. SAFETY ASSESSMENTS

Safety data will be summarized for the safety population. Table 2 summarizes the safety analyses to be performed.

Adverse events will be coded in accordance with the MedDRA. Severity of AEs will be graded by the investigator according to the NCI-CTCAE v4.03 for non-hematological AEs and IWCLL 2008 guidelines for hematologic toxicity.

Treatment-emergent period is defined as the period from the date of the first dose of study treatment up to 30 days after the date of the last dose of study treatment or the day before initiation of subsequent antineoplastic therapy (including the cross-over ibrutinib monotherapy for arm B subjects), whichever comes first.

The treatment-emergent adverse events (TEAE) are those events that occur or worsen during the treatment-emergent period or that are related to the study treatment. Unless otherwise specified, only TEAEs will be included in the adverse event summaries.

All laboratory values will be converted to and reported as international standard (SI) units. In general, only data from the central laboratory will be summarized and analyzed. Hematologic parameters including platelet counts, hemoglobin, and neutrophils will be assessed by the grading scale for hematologic toxicity in CLL studies in the IWCLL 2008 guidelines. All other gradable laboratory parameters will be graded using the NCI CTCAE v4.03. Unless otherwise specified, only baseline and post-baseline values collected during the treatment-emergent period will be included in the safety analysis.

Table 2: Summary of Safety Assessments

Assessment Type	Definition	Analysis Methods
AE	TEAEs, SAEs, Grade 3 or worse TEAEs, related TEAEs, TEAEs leading to treatment discontinuation, TEAEs leading to dose reduction, TEAEs leading to death, protocol-defined events of special interest and other safety observations. TEAEs within the first 9 months of study treatment and TEAEs in the crossover period	Descriptive summary statistics and/or listings
Lab	Worst post-baseline toxicity grade for selected CTCAE gradable hematology and chemistry. Abnormalities in creatinine clearance, uric acid, and liver function	Descriptive summary statistics and/or listings
Vital Signs and other Observations Related to Safety	Blood pressure, heart rate, new or worsened eye-related symptoms	Descriptive summary statistics and/or listings

TEAE= treatment-emergent adverse event; SAE= serious adverse event; CTCAE= Common Terminology Criteria for Adverse Events.

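### Overall TEAE tables compare about 3 to 4 times more time at risk in Arm A with Arm B; the 9-month table removes most of this but not all, and no exposure-adjusted safety summary is named

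*SAP*

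**What the plan says.** **Window.** SAP section 5 sets the treatment-emergent window as "from the date of the first dose of study treatment up to 30 days after the date of the last dose of study treatment". It closes sooner, on the day before subsequent therapy (cross-over ibrutinib included), if that is earlier. Events outside it also count if they worsened within it "or that are related to the study treatment".

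**Counting.** Protocol 10.8.1: "Multiple occurrence of the same event in a given subject will be counted once at the maximum severity".

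**Treatment length.** Chlorambucil is given "on Days 1 and 15 of each cycle, for up to 6 cycles" (SAP 1.1), and obinutuzumab for six cycles in both arms. For Arm A, Protocol 5.2.1 says "There is no prospective limitation to the duration of ibrutinib therapy".

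**Tables.** SAP Table 2 lists the usual overall TEAE categories and adds "TEAEs within the first 9 months of study treatment and TEAEs in the crossover period". The method given is "Descriptive summary statistics and/or listings". Treatment duration is summarised under SAP 3.1 and 3.4, but no section connects it to adverse event counts.

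**Purpose.** Comparing safety and tolerability between the arms is a secondary objective (Protocol 2.2).

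**The concern.** A subject watched for longer has more chance of a first event. With once-per-subject counting, the percentage can only rise as the window lengthens. Arm B's window normally closes near month 6, while Arm A's stays open for as long as ibrutinib continues.

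For an event that can occur at any time on treatment, Arm A would therefore tend to show the higher percentage even if both arms had the same rate. The overall tables alone do not tell a reader how much of an Arm A excess is risk and how much is longer observation. That matters for an objective worded as a comparison, and for the event of special interest, major hemorrhage, which Protocol 11.4.6.1 defines through treatment-emergent events.

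**Working it through.** **Inputs.** From SAP 1.4: 212 subjects, 18 per month, 1:1, analysis at about 36 months, Arm B median PFS 27 months, and "Target hazard ratio of 0.55, which corresponds to median PFS of 49.1 months for Arm A". From Protocol 8.2: 28-day cycles. The documents give no rate of stopping treatment for reasons other than progression or death. I assume 0%, 1% or 2% per month in Arm A and, in step 5, 1-4% per month in Arm B. One month is 30.44 days.

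**1. The plan's own figure.** Freedman's formula gives (1.960 + 0.842)² × (1.55/0.45)² = 7.85 × 11.86 = 93.1, rounded up to 94 events, as stated. Accrual lasts R = 212/18 = 11.8 months. With exponential PFS at hazard λ, the expected event fraction at T = 36 is 1 − (e^(−λ(T−R)) − e^(−λT))/(λR). This is 0.346 in Arm A and 0.537 in Arm B, so 106 × (0.346 + 0.537) ≈ 93.5 events. The design inputs reproduce.

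**2. Arm B window, on schedule.** The last dose is Cycle 6 Day 15, which is day 5 × 28 + 15 = 155. Adding 30 gives day 185, or 6.08 months.

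**3. Overall table, Arm B on schedule.** Let μ = ln 2/49.1 − ln(1 − s), where s is the assumed monthly stopping rate. Mean ibrutinib exposure is (1/μ) × [1 − (e^(−μ(T−R)) − e^(−μT))/(μR)].

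| s per month | Mean exposure at 36 months | Ratio to 6.08 |
|---|---|---|
| 0% | 24.5 | 4.0 |
| 1% | 21.3 | 3.5 |
| 2% | 18.7 | 3.1 |

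Counting the 30-day tail in Arm A as well adds about 0.05-0.12 to each ratio. At the 4-year final analysis (SAP 1.5.3), the same formula with T = 48 gives 5.2, 4.3 and 3.7.

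**4. The 9-month table, Arm B on schedule.** Nine months is 274 days. A subject who completes nine months on ibrutinib gives 274/185 = 1.48. On average, (1 − e^(−9μ))/μ = 8.45, 8.09 or 7.74 months, so the ratios are 1.39, 1.33 and 1.27.

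**5. Arm B also allowed to stop early.** Arm B treatment also ends at progression or unacceptable toxicity (Protocol 5.2). Let ν = ln 2/27 − ln(1 − s_B) and L = 154/30.44 = 5.06 months from first to last dose. Mean time at risk is (1 − e^(−νL))/ν + 0.99, which is 5.61 months at 1% and 5.28 at 4%. With the 30-day tail counted in both arms, Arm A means are 24.8 (s = 0) and 19.3 (s = 2%).
- Overall ratio: from 19.3/5.61 = 3.4 to 24.8/5.28 = 4.7.
- 9-month table: from 7.99/5.61 = 1.42 to 8.56/5.28 = 1.62.

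**6. Illustration only; the hazards are assumed.** Take an event seen in 20% of on-schedule Arm B subjects, with the same hazard in both arms over the first 6.08 months: −ln(0.8)/6.08 = 0.0367 per month.
- Constant hazard: about 45-56% of Arm A in the overall table at 36 months, and 24-27% in the 9-month table.
- Hazard halved after month 6.08: about 34-42% and 21-23%.

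The documents do not establish the shape of any hazard, so the distortion in the 9-month table could be small.

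**The case against.** The strongest reply is that the SAP has already dealt with this. The 9-month table takes the ratio from 3-4 down to about 1.3-1.6. Treatment duration is reported, and the overall and 9-month tables together show roughly how much of the Arm A count arises later. The tables are descriptive, and cumulative on-treatment incidence is a legitimate description of what each regimen costs a patient. Table 2 is an outline whose wording could cover person-time rates, and Protocol 10.8.1 itself speaks of incidence rates.

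Much of this stands, and it is why the priority is modest. It does not close the gap. An on-schedule Arm B subject contributes almost nothing between about month 6 and month 9. Events in Arm A after month 9, where most ibrutinib exposure lies, get a count but no rate. The protocol's incidence wording has no stated denominator, and once-per-subject counting points to simple percentages.

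Two further defences do not hold.
- **Related events.** A reader might infer that they escape the problem because they count whatever their date. Under Protocol 11.4.2, after 30 days only related serious events are still reported, and related events in Arm A accrue for as long as ibrutinib continues.
- **Dose holds.** A reader might infer that holds lengthen Arm B's window. The protocol caps their length but does not say that later doses shift. Section 8 anchors visits to Cycle 1 Day 1, and section 5.3.2.5 has some delayed Cycle 1 doses skipped.

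**Conclusion.** The point holds as a low-cost improvement. At 36 months, Arm A's mean time at risk is about 3-4 times Arm B's if Arm B completes on schedule, and about 3.4-4.7 times with Arm B progressions and early stops. In the 9-month table it is 1.48 for a completer against an on-schedule Arm B subject. On average it is about 1.3-1.4 with Arm B on schedule, or 1.4-1.6 with early stopping. These figures rest on the design PFS and on assumed stopping rates.

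A reader might go further and infer that the SAP rules out exposure-adjusted summaries, or that any Arm A excess would be an artefact. The documents support neither: the summaries are unnamed, not excluded, and true event rates are unknown.

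Infusion reactions and other Cycle 1 events are little affected. Both arms have the same obinutuzumab schedule, and Protocol 1.3.3 places infusion reactions mainly at the first infusion. Infusion-related reactions are also the one safety endpoint in the tested hierarchy (SAP 1.2.2), so the formal testing is essentially untouched. New malignancies are collected through follow-up (Protocol 11.4.5), but that rule governs collection. It does not widen the TEAE window, so they are not exempt in the TEAE tables.

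**What to change.** Keep the 9-month table, with a footnote that Arm B's time at risk usually ends near month 6. Add to SAP Table 2, by arm, for Grade 3 or higher TEAEs, SAEs and events of special interest:

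- exposure-adjusted incidence: first events per 100 patient-months, with numerator and denominator both limited to the treatment-emergent period;
- cumulative time-to-first-event estimates, stating how the end of that period and death are handled.

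A table from first dose to day 185 in both arms is optional.

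The cost is a few more descriptive tables from dates already collected, with no effect on any test or alpha. Constant-rate summaries need a caveat for early-onset events, because a long Arm A denominator dilutes them. A day-185 table would omit any Arm B on-treatment events that fall later, most of which the 9-month table would still show.

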### 1.2.4. Risks

#### 1.2.4.1. Bleeding-related Events

There have been reports of hemorrhagic events in subjects treated with ibrutinib, both with and without thrombocytopenia. These include minor hemorrhagic events such as contusion, epistaxis, and petechiae; and major hemorrhagic events, some fatal, including gastrointestinal bleeding, subdural intracranial hemorrhage, and hematuria. Use of ibrutinib in subjects requiring other anticoagulants or medications that inhibit platelet function may increase the risk of bleeding. Subjects with congenital bleeding diathesis have not been studied. See Section 6.2.3 for guidance on concomitant use of anticoagulants, antiplatelet therapy and/or supplements. See Section 6.4 for guidance on ibrutinib management with surgeries or procedures. In an in vitro platelet

function study, inhibitory effects of ibrutinib on collagen-induced platelet aggregation were observed, refer to Section 6.2.3.

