2. GENERAL ANALYSIS CONSIDERATION

2.1. Analysis Sets

Intent-To-Treat (ITT) population: defined as all subjects who were randomized. Subjects will be grouped according to the treatment assigned at randomization. This population will be the primary population for the analyses of efficacy endpoints, disposition, demographics and baseline characteristics, baseline disease characteristics, subsequent anticancer therapy and patient-reported outcome data.

Safety population: defined as all subjects who received at least 1 dose of any one of the three study drugs (ibrutinib, chlorambucil, or obinutuzumab). Safety data will be analyzed as treated. The Safety Population will be used to summarize the safety (including dosing and concomitant medications) data.

High risk analysis set: defined as randomized subjects with del17p or TP53 mutation or del 11q at baseline per central lab results.

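### The SAP plans a summary of treatment-emergent events on crossover ibrutinib, but its only treatment-emergent period closes before crossover begins, so only events judged related can qualify

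*SAP*

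**What the plan says.** SAP section 1.1 describes the crossover: "Upon IRC-confirmed progression, subjects in Arm B have the opportunity to receive ibrutinib monotherapy". SAP section 5 then sets four rules that have to be read together.

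- **Period.** "Treatment-emergent period is defined as the period from the date of the first dose of study treatment up to 30 days after" the last dose, or until "the day before initiation of subsequent antineoplastic therapy (including the cross-over ibrutinib monotherapy for arm B subjects), whichever comes first".
- **TEAE.** Treatment-emergent events are "those events that occur or worsen during the treatment-emergent period or that are related to the study treatment".
- **Scope of summaries.** "Unless otherwise specified, only TEAEs will be included in the adverse event summaries".
- **Planned output.** The adverse-event row of Table 2 includes "TEAEs within the first 9 months of study treatment and TEAEs in the crossover period", to be reported by descriptive statistics, listings or both.

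Protocol section 10.8.1 also closes its window when new anticancer therapy starts and makes the same exception for related events. Protocol Appendix I schedules adverse-event collection at the visits during next-line ibrutinib and at its end-of-treatment visit.

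**The concern.** The planned crossover summary uses a term whose definition excludes the crossover period. A programmer who follows the SAP literally would include only events the investigator judged related. One who departs from it must choose a start date, an end date and a baseline that are written nowhere, at a time when the data may already be visible.

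Relatedness is a weak filter here. The study is open-label, and the causality scale in protocol section 11.1.4 permits a judgement of not related when another cause is more plausible. Subjects are 65 or older, or younger with comorbidity, reduced creatinine clearance or a 17p/TP53 abnormality, so other plausible causes will be common. The protocol's own risk section says of bleeding: "There have been reports of hemorrhagic events in subjects treated with ibrutinib, both with and without thrombocytopenia". Each limb of the major-hemorrhage definition in protocol section 11.4.6.1 also requires the event to be treatment-emergent. A serious bleed on crossover ibrutinib that is judged unrelated would therefore fall outside that category as well.

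**Working it through.** **No published figure to reproduce.** The check is one of definitions and dates.

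**Step 1: the period.** Let L be the date of the last dose of study treatment and X the date of the first crossover dose. The SAP rule gives

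end of period = min(L + 30 days, X − 1 day) ≤ X − 1 day.

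- If L is the last dose of randomised treatment, the period ends at L + 30 or X − 1, whichever is earlier.
- If crossover ibrutinib is itself read as study treatment, L + 30 falls after X, but the earlier date still governs, so the period ends at X − 1.

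On either reading the overlap with a crossover period starting on X is zero days.

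**Step 2: which crossover events are TEAEs.**

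| Event starts or worsens on or after X | In the period? | TEAE under the SAP? |
|---|---|---|
| Judged unrelated | No | No |
| Judged related to study treatment | No | Yes, through the relatedness route only |

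**Step 3: does other text supply a window?**

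- The unless-otherwise-specified wording would let a summary include non-TEAEs. The crossover item asks for TEAEs and specifies no other window.
- Protocol section 10.8.1 has no crossover window. It has an untimed sentence about events present at baseline that worsen, but that does not reach events that are new on crossover, and the SAP ties worsening to the period.
- I found no crossover period, second window or crossover baseline elsewhere in either document.

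**Step 4: is the relatedness route clear?** SAP section 5 classes crossover ibrutinib as subsequent antineoplastic therapy. Three places point the other way: SAP section 1 uses study drug and study treatment interchangeably, SAP section 2.1 names ibrutinib among the three study drugs, and Appendix I lists crossover ibrutinib under study drug administration. The weight of the text favours counting it as study treatment, but the SAP does not say so.

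**Step 5: how many subjects could be affected by month 36.** Inputs from SAP section 1.4: 212 subjects randomised 1:1, 18 enrolled per month, Arm B median PFS 27 months, exponential PFS, analysis at about 36 months.

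- Arm B size: 212 / 2 = 106.
- Accrual: 212 / 18 = 11.8 months.
- Mean potential follow-up: 36 − 11.8 / 2 = 30.1 months.
- Expected Arm B PFS events: 106 × (1 − 2^(−30.1/27)) = 106 × 0.54 ≈ 57.

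This is an upper bound on the expected number of crossover subjects at that date. It includes deaths without progression. Crossover also requires IRC-confirmed progression that meets criteria for treatment, medical monitor or sponsor approval, and the clinical conditions in protocol section 8.4.1.

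**The case against.** The strongest reply is that the period stops at crossover for a good reason: it keeps post-crossover events out of the Arm B randomised-phase tables. Table 2 then lists crossover as its own item, and the natural reading is events emergent relative to crossover ibrutinib. A separate window was probably intended. That is fair as to intent, but the window is not written, and the one written definition gives a different table.

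Two further replies stand. The output is descriptive, in a selected, non-randomised subset. And protocol section 10.8.1 plans by-subject listings of fatal events and non-fatal SAEs without restricting them to TEAEs, so serious crossover events may still appear there. Those listings would not replace the crossover summary or show non-serious events.

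A reader might infer more than the documents support:

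- **That a given share of crossover events, or all of them, is lost.** The documents give no figure for the share judged related. Total loss would require reading study treatment as the randomised drugs only, and the text leans against that.
- **That leaving out crossover hematology is an error.** Table 2 plans no crossover laboratory summary, so the laboratory rule contradicts nothing.
- **That the comparison with Arm A is spoiled.** No comparison of crossover events with Arm A is planned.

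**Conclusion.** The point holds as an internal inconsistency in SAP section 5. Under the written definitions, the planned crossover summary admits only events judged related to study treatment and leaves out crossover events judged unrelated. This conclusion rests on the text alone and needs no numerical assumption.

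Its reach is modest. By month 36 it concerns at most about 57 Arm B subjects in expectation, given the SAP's accrual, median and exponential assumptions and 212 subjects, and fewer once deaths and the crossover criteria are taken into account. Crossover after that date is not counted. The PFS and OS analyses, alpha, power and the randomised safety comparison are unaffected. It should be corrected because a stated rule produces the wrong table, not because it threatens the trial's main conclusions.

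**What to change.** In SAP section 5:

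1. Define a crossover treatment-emergent period for Arm B: from the first dose of next-line ibrutinib to 30 days after its last dose or the day before the next antineoplastic therapy, whichever is first.
2. Base the Table 2 crossover summary on all events that start or worsen in that period, regardless of relatedness, with status before the first crossover dose as baseline.
3. State whether crossover ibrutinib counts as study treatment when relatedness is judged. If it does, say which summary a related crossover event belongs to, because the general definition would otherwise also make it a TEAE for the main Arm B tables.

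The cost is a few sentences and some programming. The on-crossover adverse events are already scheduled for collection in Appendix I. One practical check is needed: the Appendix I adverse-event row appears to begin with the treatment visits, so the sponsor should confirm which records will supply the pre-crossover baseline. The change affects reporting only, not treatment or clinical management.
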